1.4.1 Risk Assessment

Potential Risk of Clinical Significance	Summary of Data/Rationale for Risk	Mitigation Strategy
Study Intervention - Azacitidine		
Neutropenia and severe infections	In subjects randomized to oral azacitidine 300 mg at 21-day treatment schedule, the most frequent hematological AEs were neutropenia, febrile neutropenia,	To mitigate risk of severe infections, during Cycles 1 and 2 (higher risk period for severe infections) the subjects will receive oral azacitidine for 14 days of a 28-day cycle

Potential Risk of Clinical Significance	Summary of Data/Rationale for Risk	Mitigation Strategy
	
and associated infections. There was an imbalance in incidence of death between the drug and placebo treatment groups. Most of the death cases in the oral azacitidine-treated subjects occurred during the first 56 days on treatment with infections being the leading cause of death. Affected subjects showed lower median ANC at baseline, which could have made them more susceptible for severe infections.
	
schedule. The treatment can be extended to a 21-day schedule after Cycle 2, if a subject did not experience Grade 3 or 4 toxicities requiring dose delay or reductions and if there is no evidence of hematological improvement on 14-day dosing schedule.
 
During the first 2 cycles on treatment subjects' blood counts will be monitored on weekly basis, reducing to biweekly monitoring up to Cycle 12.
 
Guidance for IP dose modification due to toxicities including neutropenia and febrile neutropenia is provided in Section 8.2.4 and Table 2 of the Protocol.
 
A strong recommendation regarding administration of prophylactic fluoroquinolone antibiotics or other recognized prophylactic antibiotics was provided for subjects who develop Grade 4 neutropenia (see Section 9.1).

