- a. The study visit window for visit related assessments in the double-blind treatment phase is ± 3 days for Cycles 1 and 2; ± 7 days for Cycle 3 and beyond, unless noted otherwise for a particular assessment. **However, please note that in all circumstances a drug holiday of 7 days needs to be maintained for the treatment schedules of 300 mg and 200 mg for 21 days /28-day-cycle (14 and 21 days, respectively, for modified treatment schedules of 200 mg for 14 days/28-day-cycle and 7 days/28-day-cycle.** Study visits should also take into account the subject's IP supply. Only 1 cycle of IP will be dispensed to the subject on Day 1 of each cycle. Day 1 of Cycles 2 and beyond may be delayed from Day 28 of the prior cycle in order for subjects to recover from toxicity and meet criteria for re-treatment ([Section 8.2.5](#)). During follow-up, the study visit window is ± 7 days for visits scheduled monthly (including the follow-up visit 28 days after last dose if necessary) or ± 14 days for visits scheduled every 3 month. One cycle (one month) is considered as 28 days (ie, 4 weeks).
- b. First dose of IP in Cycle 1 should be administered within 3 days of randomization and can be on the same day of randomization.
- c. All subjects who have received at least one dose of IP should undergo Treatment Discontinuation procedures detailed in [Section 6.13](#) when treatment is discontinued. The reason for discontinuation will be recorded in the CRF and in the source document for all randomized subjects, regardless of whether they are dosed or not. Reasons for discontinuation are provided in [Section 12](#).
- d. MDS diagnosis, WHO classification ([Appendix A](#)), and IPSS risk classification ([Appendix B](#)) will be prospectively determined by independent central pathology and cytogenetics review, and applicable central laboratory results. Thus bone marrow aspirate and biopsy samples together with peripheral blood samples must be collected at screening as detailed in [Section 6.1.1](#). At all later time points a biopsy is only needed if adequate aspirate is not attainable. Blood samples at screening should be collected on the same day as the bone marrow aspirate/biopsy procedure. Instructions for submission of bone marrow slides, sample collection, processing, storage, and shipment procedures are provided in the study's Central Laboratory Manual.

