6.6.5 Hematology and Serum Chemistry Laboratory Evaluations

Hematology and serum chemistry laboratory analyses must be performed according to [Table 1](#). The same parameters as required at screening should be evaluated (see [Section 6.1](#) for details regarding the parameters for hematology and serum chemistry, respectively).

The hematology samples will be collected prior to IP administration and will be analyzed by the central laboratory. The frequency of hematology assessment in the treatment phase is as such: weekly on Day 1, 8, 15 and 22 in Cycles 1-2, and biweekly on Day 1 and 15 in Cycles 3-12, and monthly on Day 1 thereafter and at Treatment Discontinuation.

The serum chemistry samples will be collected prior to IP administration and will be analyzed by the central laboratory. The frequency of serum chemistry assessment in the treatment phase is as such: weekly in Cycles 1-2 and monthly on Day 1 thereafter, and at Treatment Discontinuation.

On a case-by-case basis and at the investigator's discretion, the Day 8, 15, and 22 hematology and serum chemistry draws may be performed at the subject's local/primary physician office and shipped to the central laboratory for analysis or obtained via an in-home nursing service (where

available). In these specific cases, the sponsor needs to be consulted prior to performing these blood draws to assess logistics and obtain local laboratory details. In addition, to ensure the medical care of the individual study subject is maintained, the investigator remains responsible for all subject procedures performed during the study and communication with the subject must be continued. Proper documentation is required in the source documents at the investigative site in these cases.

Any or all laboratory assessments may be repeated more frequently if clinically indicated. In the event that an immediate laboratory assessment is required to acutely manage a subject, local laboratory tests may be used. In addition to collecting the local laboratory sample, a second sample should be collected and sent to the central laboratory.

Refer to [Section 11.3](#) for guidance on abnormal laboratory values and test results.

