6.7.5 International Working Group Response/Improvement

Response/improvement assessment according to the International Working Group (IWG) criteria (Cheson, 2006; Appendix D) is to be performed on Day 1 of Cycles 3, 6, and 12, and every 6 cycles thereafter (eg, Day 1 of Cycles 18, 24, etc.) and recorded on the CRF. Due to the turnaround time required to obtain results from the central review of bone marrow aspirate (or biopsy if adequate aspirate is not attainable), peripheral blood smear and cytogenetics, IWG response/improvement assessment could be done at any time prior to starting the next cycle (eg, prior to starting Cycles 4, 7, 13, etc., respectively).

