Step 2: For subjects who don’t have baseline value from Step 1, apply the “7/3-day rule”. Use the lowest value among the Hgb values from the Central lab which are collected within 7 days after a RBC/whole blood transfusion and within 3 days before another transfusion as the baseline value. The rationale is that the Hgb value within 7 days from the first transfusion was only somewhat influenced by that transfusion.

Step 3: For subjects who don’t have baseline values from Steps 1 and 2, use the lowest value among all Hgb values from the Central lab which are collected on or prior to Cycle 1 Day 1.

The baseline values for platelet count will be determined similarly to eliminate the impact of platelet transfusion.

For absolute neutrophil count, white blood cell count and bone marrow blasts, the baseline values will be determined by selecting the last non-missing value from the Central lab on or prior to Cycle 1 Day 1. In case that a randomized subject was not treated (no Cycle 1 Day 1 date), the date of randomization will be used.

Baseline transferrin saturation will be derived using the serum samples collected at screening. The transferrin saturation result is derived as: iron (umol/L) / total iron binding capacity (umol/L). In case the result of total iron binding capacity is reported as “<xxx”, xxx-1 will be used as the total iron binding capacity to derive the transferrin saturation.

By-subject listings of the baseline disease characteristics will be provided.

In addition to the above baseline disease characteristics, the revised international prognostic scoring system for MDS (IPSS-R, [Greenberg, 2012, Appendix G](#)) will be summarized for exploratory purpose.

IPSS-R score will be classified and summarized as: very low, low, intermediate, high, very high. The derivation for the IPSS-R score is provided in [Appendix G](#). The revised IPSS cytogenetic classification (from central lab) will also be summarized (very good, good, intermediate, poor, very poor).

[REDACTED]

By-subject listings of IPSS-R will be provided.

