18.5. Appendix E: Hematologic Response According to the IWG Criteria for MDS

Modified Hematologic Response According to IWG Criteria for MDS	
Category	Response criteria (responses must last at least 4 weeks)
Complete Remission (CR)	Bone marrow: $\leq 5\%$ myeloblasts with normal maturation of all cell lines ^a Persistent dysplasia will be noted ^{a,b} Peripheral blood ^c Hgb ≥ 11 g/dL Platelets $\geq 100 \times 10^9/L$ Neutrophils $\geq 1.0 \times 10^9/L^b$ Blasts 0%
Partial Remission (PR)	All CR criteria if abnormal before treatment except: Bone marrow blasts decreased by $\geq 50\%$ over pretreatment but still $> 5\%$ Cellularity and morphology not relevant
Marrow CR ^b	Bone marrow: $\leq 5\%$ myeloblasts and decrease by $\geq 50\%$ over pretreatment ^b Peripheral blood: if HI responses, they will be noted in addition to marrow CR ^b
Stable Disease (SD)	Failure to achieve at least PR, but no evidence of progression for > 8 wks
Failure	Death during treatment or disease progression characterized by worsening of cytopenias, increase in percentage of bone marrow blasts, or progression to a more advanced MDS FAB subtype than pretreatment
Relapse After CR or PR	At least 1 of the following: Return to pretreatment bone marrow blast percentage Decrement of $\geq 50\%$ from maximum remission/response levels in granulocytes or platelets Reduction in Hgb concentration by ≥ 1.5 g/dL or transfusion dependence
Cytogenetic Response	Complete - Disappearance of the chromosomal abnormality without appearance of new ones Partial - At least 50% reduction of the chromosomal abnormality
Disease Progression	For subjects with: Less than 5% blasts: $\geq 50\%$ increase in blasts to $> 5\%$ blasts 5%-10% blasts: $\geq 50\%$ increase to $> 10\%$ blasts 10%-20% blasts: $\geq 50\%$ increase to $> 20\%$ blasts 20%-30% blasts: $\geq 50\%$ increase to $> 30\%$ blasts Any of the following: At least 50% decrement from maximum remission/response in granulocytes or platelets Reduction in Hgb by ≥ 2 g/dL Transfusion dependence

KEY: CR = complete remission; DFS = disease-free survival; FAB = French-American-British; Hgb = hemoglobin; HI = hematologic improvement; IWG = International Working Group; MDS = myelodysplastic syndromes; PFS = progression free survival; PR = partial remission

^a Dysplastic changes should consider the normal range of dysplastic changes (modification).

^b Modification to IWG response criteria.

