- $\geq 10\%$ - < 20% blasts: $\geq 50\%$ increase and has blasts > 20%
- $\geq 20\%$ - < 30% blasts: $\geq 50\%$ increase and has blasts > 30%

Bone marrow blasts are used.

Or with any of the following:

- a. At least 50% decrement from maximum remission / response levels in neutrophils and $< 1.0 \times 10^9 /L$;
- b. At least 50% decrement from maximum remission / response levels in platelets and $< 100 \times 10^9 /L$;
- c. Reduction from maximum remission / response levels in Hgb by ≥ 2 g/dL and < 11 g/dL;

To confirm a “disease progression”, any of the criteria (a, b and c) a subject met in a previous assessment must be kept for at least 4 weeks.

- **Stable disease:**

For at least 8 weeks, failure to achieve at least mCR, but no evidence of progression.

- **Failure due to death:**

- Death during treatment; AND
- No post-baseline efficacy assessments are available; i.e., no bone marrow or hematology available.

- **Not evaluable:**

- Subject withdrew consent or was lost to follow-up, AND
- Subject was alive at last contact, AND
- No post-baseline efficacy assessments are available; i.e., no bone marrow or hematology available.

- **Relapse after CR or PR:**

A subject is considered having “Relapse after CR or PR” if any of the following is met:

- Return to pretreatment (baseline) bone marrow blast percentage;
- At least 50% decrement from maximum remission / response levels in neutrophils and $< 1.0 \times 10^9 /L$;
- At least 50% decrement from maximum remission / response levels in platelets and $< 100 \times 10^9 /L$;
- Reduction in Hgb concentration from maximum remission / response levels by ≥ 1.5 g/dL and < 11 g/dL or transfusion dependence

To confirm a “relapse”, the criterion a subject met in a previous assessment must be met for at least at least 4 weeks. Subjects will not be evaluable for relapse after CR or PR if no 4 weeks data available.

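### SAP 18.6.1 counts an on-treatment death as Failure only when no post-baseline marrow or blood count exists, which contradicts Appendix E and keeps most early deaths out of the derived Failure row

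*SAP*

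**What the plan says.** SAP 10.2.15 defines hematologic response, Failure included, by the IWG 2006 criteria in Appendix E. There, Failure is "Death during treatment or disease progression characterized by worsening of cytopenias", an increase in marrow blasts, or a move to a more advanced subtype. No condition on missing data is attached to death. Protocol Appendix D has the same definition.

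SAP 18.6.1 then gives the rules for deriving response from central laboratory data. Its category for failure due to death has two parts: "Death during treatment; AND" and "No post-baseline efficacy assessments are available; i.e., no bone marrow or hematology available". The neighbouring progression rule is labelled as modified from IWG; the death rule carries no such label. SAP section 16 does not list it and states that there are no further changes to the protocol's analyses.

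On timing, Protocol 6.6.5 schedules hematology "weekly on Day 1, 8, 15 and 22 in Cycles 1-2". On deaths, Protocol 1.4.1 reports an imbalance between the arms and adds: "Most of the death cases in the oral azacitidine-treated subjects occurred during the first 56 days on treatment".

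**The concern.** Two parts of one SAP give different definitions of Failure. The narrower one applies only to subjects with no data after baseline, and with weekly sampling that group is almost empty after the first week or so on treatment. The window in which the rule stops recognising deaths is the window in which the protocol says most azacitidine-arm deaths occurred. At stake is the derived Failure row: it would show few of the early deaths that Appendix E assigns to it, and the shortfall would probably be larger on azacitidine. A reader comparing the arms on that row would see too small a difference.

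**Working it through.** The plan states no figure on this point, so there is none to reproduce. The check has two parts.

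**1. Where can an early death go under SAP 18.6.1?**

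The inputs are these. Baseline for neutrophils, white cells and marrow blasts is "the last non-missing value from the Central lab on or prior to Cycle 1 Day 1" (SAP 8.2), and hemoglobin and platelets use the same cut. The first post-baseline count is therefore due on Day 8. The visit window is ± "3 days for Cycles 1 and 2" (Protocol Table 1, footnote a), which gives Day 5 to Day 11. On-treatment marrow is first scheduled at Cycle 3 Day 1, about Day 57 (Table 1, footnote t).

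| Derived category | Requirement | Open to a death by Day 56? |
|---|---|---|
| Failure due to death | No post-baseline marrow or hematology | Only before the first count |
| CR, PR | Criteria held for 4 weeks, with a post-baseline marrow change | Not without an off-schedule marrow |
| mCR | Two consecutive marrow results | Not on schedule |
| Stable disease | At least 8 weeks | No |
| Not evaluable | Withdrew or lost to follow-up, and alive at last contact | No |
| Progression on counts | Fall kept for at least 4 weeks | From about Day 8 + 28 = Day 36 |
| Progression on blasts | Marrow result | Only with a marrow taken unscheduled or early in its window |

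The count-based route is narrower still, because SAP 18.6 disallows hemoglobin and platelet values within 7 days after the relevant transfusion, and this population is transfusion-dependent.

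So, taking the first count on Day 8 and no missed samples:
- a death on Days 1-7 is Failure due to death;
- a death on Days 8-35 has no derived category unless a marrow shows progression;
- a death on Days 36-56 can otherwise enter only as count-based progression kept for 4 weeks.

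**2. What share of deaths in Days 1-56 is left out of the Failure row?**

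The timing of deaths is an assumption. Let w(d) be the weight of death on day d, k(d) the number of counts due by day d (Days 8, 15, 22, 29, 36, 43 and 50, all shifted by -3, 0 or +3 days), and m the chance that any one sample is missing. The share still classed as Failure is Σ w(d)·m^k(d) / Σ w(d).

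With m = 0 this is the weight falling before the first count. For the two sloped shapes the weights sum to 56 × 57 / 2 = 1,596.

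| Assumed timing | First count Day 5 | Day 8 | Day 11 | Left out |
|---|---|---|---|---|
| Uniform, w = 1 | 4/56 = 7.1% | 7/56 = 12.5% | 10/56 = 17.9% | 82-93% |
| Front-loaded, w = 57 - d | 218/1,596 = 13.7% | 371/1,596 = 23.2% | 515/1,596 = 32.3% | 68-86% |
| Back-loaded, w = d | 10/1,596 = 0.6% | 28/1,596 = 1.8% | 55/1,596 = 3.4% | 97-99% |

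With m = 0.3, uniform timing and a Day 8 first count, 17.9% are classed as Failure and 82% are left out. The least unfavourable case examined (front-loaded, Day 11, m = 0.3) gives 39.8% classed and 60% left out.

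Under uniform timing with a Day 8 count, the excluded 87.5% divides into 28/56 = 50% (Days 8-35) and 21/56 = 37.5% (Days 36-56).

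**The case against.** Several points on the other side have force.

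- **Response rates are unaffected.** Efficacy is analysed on ITT (SAP section 10), so a subject with no derived label still counts as a non-responder. CR, PR, mCR, SD and HI rates are not inflated in either arm. This stands.
- **The investigator's assessment is summarised too.** SAP 10.2.15 first tabulates every category, Failure included, from the IWG response CRF. It then lists what is derived from central labs, and that list omits Failure and progression. The 18.6.1 row might therefore be only a reason why no response could be derived. This stands in part: 18.6.1 does write rules for both omitted categories, so the SAP is inconsistent on what will be shown. Nor is the CRF a dependable backstop. IWG assessment "is to be performed on Day 1 of Cycles 3, 6, and 12, and every 6 cycles thereafter" (Protocol 6.7.5), and Table 1 shows none at Treatment Discontinuation. The CRF may capture some early deaths, but no scheduled assessment prompts the entry. It would go too far to say that it misses them, since its completion rules are not in the documents.
- **The deaths are reported elsewhere.** They appear by arm in OS (SAP 10.2.1), in TEAEs leading to death, including for Cycles 1-2 (11.1 and 11.1.1), and in cause of death by treatment period (11.2). This stands.
- **The endpoint is descriptive** and outside the alpha-controlled tests. This stands.
- **The wording could mean that either marrow or hematology is missing.** On that reading most early deaths would qualify, since few would have a marrow. But the lead clause speaks of no efficacy assessments at all, and a subject with weekly counts has some. SAP section 6 uses a broader meaning of the same term, in which a transfusion alone counts, and that would shrink the category further.

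**Conclusion.** The contradiction is real and undeclared. Applied as written, SAP 18.6.1 leaves about 82-93% of deaths in Days 1-56 out of the derived Failure row under uniform timing with complete sampling. The range is 68-99% across the assumed timings, and 60% at the lowest with 30% of samples missing. These shares rest on assumed death times. The number of subjects cannot be computed, because the documents give no count of early deaths. That the shortfall is larger on azacitidine is probable rather than shown: it follows from the imbalance and early clustering described without numbers in Protocol 1.4.1.

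A reader might infer that early deaths vanish from the response table, or that the comparison of hematologic response is biased in favour of azacitidine. The documents do not support either. The subjects remain in every ITT denominator, no response rate changes, and the distortion is confined to one row of a descriptive derived table.

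**What to change.** 1. In SAP 18.6.1, remove the no-assessment condition from the failure-due-to-death category. A death during treatment without an earlier qualifying best response (CR, PR, mCR, or stable disease of at least 8 weeks) is then Failure. Keep the condition for Not evaluable.
2. State that this best-response ordering is the SAP's own convention for applying Appendix E, which has no 8-week limit on deaths. Say explicitly that a death preceded by derived progression is Failure under this rule.
3. Name Failure and progression in the list of derived categories in 10.2.15.
4. Declare the rule in section 16.
5. Add a residual row so that the categories sum to the ITT count in each arm. It is needed even after step 1, because subjects who leave treatment alive before 8 weeks with counts on file also have no category.

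The cost is a few lines of SAP text and a re-run of one descriptive table from data already held. Because the primary clinical study report is final (rationale for Protocol Amendment 6.0), the result would be a labelled supplementary table. The downside for the sponsor is a less favourable Failure count in the active arm.

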18.6.2. Cytogenetic response (Complete or Partial)

1. At each time point, Abnormality Rate = (abnormal_metaphases / metaphases_analyzed) * 100%;
2. The abnormality rate at the screening visit is considered as the baseline abnormality rate, in case there are multiple records, use the one with the larger “metaphases_analyzed”;
3. Only the subjects with non-zero baseline abnormality rate will be included in the analysis;
4. **Cytogenetic Complete Response (CR)** is “Yes” if the post-baseline abnormal rate is decreased to 0; in case the number of baseline “abnormal_metaphases” is ≤ 4 , the post-baseline responses from two consecutive time points will be needed to confirm a CR is “Yes” (this time point and the next time point both have 0 abnormality rate);
5. **Cytogenetic Partial Response (PR)** is “Yes” if the post-baseline abnormal rate is decreased by at least 50% from the baseline; in case the number of baseline “abnormal_metaphases” is ≤ 4 , the post-baseline responses from two consecutive time points will be needed to confirm a PR is “Yes” (this time point and the next time point both have abnormality rate decrease by at least 50% from the baseline).

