6.1.1 MDS Diagnosis, WHO Classification, and IPSS Risk Classification

MDS diagnosis, WHO classification ([Appendix A](#)), and IPSS risk classification ([Appendix B](#)) will be prospectively determined by independent central pathology and cytogenetics review, and applicable central laboratory results. Thus at screening bone marrow aspirate and biopsy samples together with peripheral blood samples must be collected. At all later time points a biopsy is only needed if adequate aspirate is not attainable.

- Morphological assessment: Slides of the bone marrow aspirate (bone marrow aspirate smears, including one for iron stain) and biopsy (touch prep smears), and peripheral blood smear will be prepared locally and sent to the central pathology reviewer for assessment.
- Cytogenetic analysis: Bone marrow aspirate (or biopsy if adequate aspirate is not attainable - note that specific handling of the biopsy is required if also to be used for cytogenetic testing [see the study’s Central Laboratory Manual for handling instructions]) will be sent to the central cytogenetic reviewer for processing and analysis prior to randomization. At least 20 analyzable metaphases are required for standard G-banding cytogenetic analyses. If, after two bone marrow aspirate and/or biopsy procedures, 20 metaphases cannot be obtained, at least 10 analyzable metaphases are required for standard G-banding cytogenetic analysis at screening.

- **Peripheral blood sample:** A peripheral blood sample will be sent to the central laboratory for a complete blood count (CBC) with white blood cell (WBC) differential and platelet count.

The screening bone marrow aspirate and biopsy samples for central pathology and central cytogenetic review, and the screening hematology samples for central laboratory analysis should be collected no later than 14 days prior to randomization in order to allow sufficient time for central review and a repeat bone marrow assessment, if necessary.

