- Language has been added to allow for the use of historical cytomorphologic, histologic and/or cytogenetic bone marrow samples to support the screening central laboratory results, which may be samples that were obtained outside of the 56 day screening window, but must be from within 3 months of the first screening bone marrow procedure.
- Language has also been added to allow for the use of fewer than than 20 analyzable metaphases in standard G-banding cytogenetic analysis at screening.

- Language has been added to allow for the use of FISH analysis to rule out common chromosomal aberrations that occur in MDS if, after two bone marrow aspirate procedures as part of screening for this study, only few (<10), or no, metaphases are able to be rendered with which the karyotype can be characterized via standard G-banding.

The to-date experience in AZA-MDS-003 has shown that 14% of subjects screened have an insufficient number of metaphase cells with which to analyze their cytogenetic status. Despite undergoing repeat bone marrow aspirates, and sometimes repeat biopsies, many patients do not have sufficient cells for adequate cytogenetic analysis in order to be evaluated for inclusion by IPSS criteria.

In addition, while bone marrow chromosome banding analyses remain the gold standard of cytogenetics in MDS patients, in the case of repeated failure of standard G-banding (absent or poor quality metaphases) FISH analysis is recommended to detect targeted chromosomal abnormalities in interphase nuclei according to the European LeukemiaNet consensus regarding diagnostic procedures for MDS (Malcovati, 2013).

Similar to the challenges in performing standard G-banding chromosomal analysis from patient samples with hypocellular /fibrotic bone marrow, clear confirmation of diagnosis of MDS by cytomorphological analysis is also limited due to the fact that MDS progresses; issues of hypocellularity and reticulin fibrosis of the marrow can occur or increase in amount. In this circumstance, confirmation of a definitive MDS diagnosis on prior marrows could enable the central pathologist to have a clearer understanding for the presence of MDS in the screening samples for this study. The 3 month window during which the historical bone marrow samples must have been obtained has been proposed to minimize the chance that the evolution of the MDS has occurred in this time period.

Revised section: 6.1.1

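### SAP 18.6.2 sets no minimum number of analysed metaphases after baseline, so the rule as written can score a poor-yield marrow as a cytogenetic response

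*SAP*

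**What the plan says.** SAP 18.6.2 defines the quantity as follows: "At each time point, Abnormality Rate = (abnormal_metaphases / metaphases_analyzed) * 100" percent. A complete response is scored "if the post-baseline abnormal rate is decreased to 0; in case the number of baseline" abnormal metaphases is 4 or fewer, "the post-baseline responses from two consecutive time points will be needed to confirm a CR is" positive. A partial response requires the rate to fall by at least half from baseline, with the same confirmation. This confirmation is the one safeguard, and it depends on the baseline count.

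Two other rules in the section concern baseline only. The analysis set is restricted there: "Only the subjects with non-zero baseline abnormality rate will be included in the analysis". For duplicate screening records the rule is "in case there are multiple records, use the one with the larger" number of metaphases analysed. SAP 10.2.15 then keeps the best response on treatment.

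Metaphase minima appear only in protocol 6.1.1, under Screening: "At least 20 analyzable metaphases are required for standard G-banding cytogenetic analyses", with a fallback after two procedures if "20 metaphases cannot be obtained, at least 10 analyzable metaphases are required for standard G-banding cytogenetic analysis at screening". Neither SAP 18.6.2, SAP 10.2.15 nor protocol 6.7.4 (on-treatment cytogenetics) carries a minimum forward, defines a not-evaluable sample, or says what to do when no metaphase was analysed (0/0).

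**The concern.** An observed rate of zero means little if few cells were counted. The SAP recognises sampling error in the baseline sample, where it prefers the larger count and asks for confirmation of small clones. A false zero, however, arises in the post-baseline sample, and there the size of the count plays no part.

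Poor yield is foreseeable in this population. In the justification for Amendment 2 the sponsor reports that "14% of subjects screened have an insufficient number of metaphase cells".

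The rule is also looser than its neighbours in SAP Appendix F. Derived complete and partial remission must hold for 4 weeks, marrow remission needs two consecutive marrows, and hematologic improvement must last 8 weeks. A cytogenetic response with 5 or more abnormal metaphases at baseline needs one sample of any size. At stake is whether the reported percentages of cytogenetic responders reflect clearance of the clone or thin samples.

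**Working it through.** The documents state no error rate or power for this endpoint, so there is no figure to reproduce. The check sizes the consequence of the rule.

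**Inputs from the documents:** the rate, the response rules and the trigger of 4 or fewer abnormal metaphases (SAP 18.6.2); best response kept (SAP 10.2.15); 20 metaphases, or at least 10, at screening (protocol 6.1.1); marrows on Day 1 of Cycles 3, 6 and 12, then every 6 months (protocol Table 1, footnote t).

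**Assumptions:** metaphases are independent draws; the true abnormal fraction p is unchanged and equals the baseline rate; post-baseline yield m is hypothetical, since no document reports it.

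**False complete response, one sample (5 or more abnormal at baseline).** P = (1 − p)^m.

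| Baseline | m = 3 | m = 5 | m = 10 | m = 20 |
|---|---|---|---|---|
| 5/20 (p = 0.25) | 0.75³ = 42.2% | 0.75⁵ = 23.7% | 5.6% | 0.3% |
| 10/20 (p = 0.50) | 12.5% | 3.1% | 0.1% | about 0 |
| 15/20 (p = 0.75) | 1.6% | 0.1% | about 0 | about 0 |

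**With the two-time-point rule (4 or fewer at baseline).** P = [(1 − p)^m]² for a given pair of samples. For 4/20: (0.8³)² = 26.2% at m = 3, 10.7% at m = 5, 1.2% at m = 10 and 0.01% at m = 20. Confirmation helps, but two thin samples still satisfy it.

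**Best of three samples, baseline 5/20.** 1 − (1 − 0.237)³ = 55.6% if all three have 5 metaphases, and 1.0% if all three have 20.

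**False reduction of at least 50%, one sample.** P(X ≤ floor(mp/2)), which includes the zero-abnormal result. For 5/20: 23.7% at m = 5, 24.4% at m = 10 and 9.1% at m = 20. For 10/20: 18.8%, 5.5% and 2.1%. At 5/20 with m = 5, floor(0.625) = 0, so this is the same event as the false complete response and must not be added to it.

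**Two consecutive samples for partial response, baseline 5/20.** 0.091² = 0.8% at m = 20; 0.244² = 6.0% at m = 10.

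**What an observed zero excludes.** The one-sided 95% upper bound is 1 − 0.05^(1/m): 63% abnormal cells for 0/3, 45% for 0/5 and 14% for 0/20.

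**The case against.** Much of the opposing case stands.

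- **Stakes.** Cytogenetic response is one component of hematologic response, presented as counts and percentages, with no planned test and outside alpha control. The response recorded on the CRF is summarised separately, so discordance with the central-laboratory derivation would be visible. The primary endpoint and OS are untouched.
- **A threshold may exist.** The 20-metaphase sentence carries no time qualifier of its own, analysis is central and standardised, and the Central Laboratory Manual is not among the documents. A laboratory adequacy limit cannot be excluded. But the sentence sits under Screening, its fallback is limited to screening, and the SAP invokes neither.
- **Yields of 3 to 5 are hypothetical.** Amendment 2 newly allowed fewer than 20 metaphases, so an insufficient sample may often have meant 10 to 19. In that range the risk of a false complete response for a 25% clone is at most 5.6% per sample.

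A reader might also draw four stronger conclusions that the documents do not support:

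- That the error favours azacitidine. No yield by arm is given. The Amendment 2 text links hypocellularity and fibrosis to progression of MDS, which could lower yield on placebo as well.
- That 14% is the failure rate after repeat procedures. It is given for screened subjects; the persistence of the problem after repeats is a separate, unquantified remark. Nor is it an on-treatment rate.
- That a single poor marrow is always enough. With 4 or fewer abnormal metaphases at baseline it is not.
- That 56% is an expected error rate. It needs a small clone and three samples of 5 metaphases.

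**Conclusion.** The gap is real and can be read from the text: the derivation places no lower limit on the post-baseline denominator, and its only safeguard looks at the wrong sample. This is more than missing detail, because following the rule exactly would turn 0 of 3 into a complete response for a subject with 5 of 20 abnormal at baseline, an outcome with probability 42% if nothing had changed. The risk falls to 5.6% at 10 metaphases and 0.3% at 20, and is small for large clones at any plausible yield (1.6% for a 75% clone with 3 metaphases). These sizes rest on binomial sampling and an unchanged clone. How often thin samples occurred on treatment, and in which arm, is unknown. The consequence is possible misclassification in a descriptive secondary endpoint, in no established direction between arms.

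**What to change.** In SAP 18.6.2:

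1. Treat a post-baseline sample as evaluable for cytogenetic response only if it meets the protocol's own minimum: 20 analysed metaphases, or at least 10. Score samples below 10, including 0/0, as not evaluable.
2. List the number of metaphases analysed, at baseline and at response, for each subject counted as a responder.
3. Show partial response confirmed at two consecutive time points as a sensitivity analysis, because a minimum alone leaves about 9% false reductions at 20 metaphases for a 5/20 clone.
4. If the central laboratory already applies an adequacy threshold, state it here; that would largely settle the point for complete response.

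The primary-analysis report is final (protocol, rationale for Amendment 6.0), so this should be run and labelled as a post hoc sensitivity re-derivation beside the planned result. The count of analysed metaphases is already a variable in the derivation, so the programming is small. The price is somewhat fewer evaluable subjects and a slightly lower response rate. Confirmation also costs some true responders: scheduled marrows are 3 to 6 cycles apart, and subjects who stop before the next one cannot be confirmed. That is why confirmed partial response is better shown as a sensitivity analysis than made the main rule.
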